8.4. Demographics and Baseline Characteristics

The age, race, ethnicity, menopausal status, breast density, and BI-RADS score will be presented using descriptive statistics for the overall ITD population, by study population type, by sites (individual, private practice, academic), by biopsy status (immediate, delayed, never), and by cancer status (benign, high risk, malignant).

8.5. Analysis Definitions

The final data for diagnostic test sensitivity and specificity will be presented in terms of a 2×2 table as follows; the threshold for defining a positive POM will be 2% corresponding to clinical practice standards:

Table 5: 2 x 2 Table

	Cancer	Benign
Test +	True Positive (TP)	False Positive (FP)
Test -	False Negative (FN)	True Negative (TN)

The above 2x2 table will also be constructed separately for Imagio and the Imagio diagnostic ultrasound component relative to a cancer or benign diagnosis. In addition, these 2x2 tables will also be generated for immediate biopsies, for delayed biopsies, for all biopsies, and for all cases including those not biopsied; discordant pairs for sensitivity as well as specificity will be analyzed. Those subjects without a biopsy will be excluded if they were not followed without a subsequent clinical evaluation.

A subject will be assigned to a row in the table depending on the respective diagnostic test result. Subjects with a diagnosis (biopsy or 11 month follow-up with no biopsy) will be assigned a column in the table according to the following rules:

- 1. If the result of the biopsy results in a cancer diagnosis, then the subject will be assigned to the Cancer column.
- 2. If the result of the biopsy results in a benign diagnosis, then the subject will be assigned to the Benign column.
- 3. If the biopsy was not performed and the subject was evaluated after 11 months post-baseline (nominal 12 month evaluation), then the subject will be counted as TN as long as there were no contrary clinical or radiologic findings (not to be based on Imagio); any mass declared to have any contrary clinical or radiologic findings will be declared to be a False-Positive if the Imagio POM was ≤2%; otherwise the subject will not be included in the table
- 4. If the baseline Imagio evaluation was not performed or declared to not be useable, then the subject will not be included in the table.

In addition, the cancer group will be further divided into invasive carcinoma and DCIS categories and each of these two categories will be assessed separately within a 2x2 table.

The use of the terms *sensitivity* and *specificity* is justified in this study because the biopsy and 11 month evaluation (12 month nominal evaluation) is the gold standard. The following statistical endpoints will be assessed for each image set:

- The true positive rate (TPR) or sensitivity of the test is defined as TP/ (TP + FN)
- The specificity of the test is defined as TN/ (TN + FP)
- The concordance of the test is defined as (TP + TN)/N
- The positive likelihood ratio is defined as TPR/FPR
- The negative likelihood ratio is defined as (1 TPR)/(1 FPR)
- The positive predictive value (PPV) is defined as TP/(TP + FP)
- The negative predictive value (NPV) is defined as TN/ (TN + FN)
- The *odds ratio* (OR) is defined as (TP/FP)/(FN/TN)

Given that biopsy decisions are made using the 2% POM, POM levels >2% have limited relevance to the 2% threshold now widely used for making biopsy decisions.

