3.4. Study Duration

Subjects are to be enrolled after decision to biopsy or not to biopsy. Each subject will undergo consent to have an Imagio evaluation, which must be completed within 10 business days of the Enrollment Visit; the Imagio evaluation must be performed prior to any biopsy. Thus all selected subjects will undergo an Imagio evaluation following conventional diagnostic ultrasound and in some cases mammography before any immediate biopsy. For subject management efficiency, once the subject agrees to participate in the study and her biopsy is scheduled, she can then be scheduled for Imagio prior to the biopsy. The subjects must have the Imagio evaluation within 45 business days before the biopsy. Core needle biopsy, image guided directional vacuum assisted needle biopsy (DVAB), or surgical biopsy will be performed. For

Seno Clinical Study Protocol: PIONEER-01
300176 Rev 8 PIONEER 01 Protocol Amendment 3.2

subjects requiring a second biopsy, additional time (up to 45 business days) will be permitted to perform the second biopsy. Any such decisions to biopsy will be made solely by the site without considering any Imagio evaluation outcomes.

All subjects not undergoing an immediate biopsy will be followed clinically for an additional 12 months. All subjects will have an Imagio evaluation at the first Imaging Visit and a subsequent Imagio evaluation before any subsequent biopsy that might be necessary because of an interval clinical finding during the 12 month follow-up or because of a 6 month follow-up conventional diagnostic ultrasound that has been recommended by the investigator. If the interval clinical problem does not result in a recommendation for biopsy, the investigator may schedule a 6 or 12 month follow-up visit at their discretion. Follow-up will end when either:

- 1. The subject undergoes a biopsy by 12 months, or
- **2.** Once the subject has been followed for at least 12 months.

Any such decisions to biopsy will be made solely by the site investigator without considering the Imagio evaluation outcome.

Each subject will attend up to 4 visits:

- A Screening Visit.
- An Enrollment Visit (Day 1).
- 1 or 2 Imaging Visits (Day 1 to Day 10; a second Imaging Visit will occur for any biopsy within 12 months for those subjects with a biopsy scheduled before the first Imaging Visit).
- A Follow-Up Visit at 12 months (if no biopsy is scheduled within 12 months of the Enrollment Visit).

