8.3. Analysis Populations

Seno Clinical Study Protocol: PIONEER-01
300176 Rev 8 PIONEER 01 Protocol Amendment 3.2

Confidential Page 54 of 80

All analyses will be performed with the intention to diagnose (ITD) study population which consists of all subjects coming in for their scheduled Imagio evaluation, having Imagio data declared evaluable, and having a biopsyat 12 months, or declared to be TN (or FP) at 12months.

There will be Truth Panel review to identify mass-specific subgroups and TN outcomes as well as reader-specific exclusions for the following:

- 1. Cases with QAR concerns (including cases with previously unidentified suspicious masses and cases where the Imagio evaluation was incomplete, unreliable, or unusable) for exclusions
- 2. Cases where the number or numbering of suspicious masses is under dispute (per QARs or IRs) for exclusions
- 3. Cases with questionable eligibility for exclusions
- 4. Cases with high risk histologies for separate analyses
- 5. Cases where individual IRs identified problems with specific image sets for exclusions
- 6. Cases with NDUs to determine if a mass was a True-Negative (TN) for specificity calculations.

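### Two sentences that set the analysis denominators (8.5 on unbiopsied women, 8.3 on biopsy timing) are misworded and contradict the protocol's other rules

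*Protocol*

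**What the plan says.** Section 8.5 has an exclusion for women who were never biopsied: "Those subjects without a biopsy will be excluded if they were not followed without a subsequent clinical evaluation". The next paragraph says who is placed in the 2x2 table: "Subjects with a diagnosis (biopsy or 11 month follow-up with no biopsy) will be assigned a column in the table". Rules 1 and 2 assign the column from the biopsy result and set no limit on when the biopsy was done ("If the result of the biopsy results in a cancer diagnosis, then the subject will be assigned to the Cancer column"; rule 2 is the same for benign). Rule 3 covers the unbiopsied and begins "If the biopsy was not performed and the subject was evaluated after 11 months post-baseline". Section 8.5 also plans separate tables for immediate biopsies, delayed biopsies, all biopsies, and all cases with the unbiopsied included.

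Section 8.3 says that all analyses use one intention-to-diagnose (ITD) population: subjects who come for the scheduled scan, "having Imagio data declared evaluable, and having a biopsyat 12 months, or declared to be TN (or FP) at 12months".

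Elsewhere, 3.4 ends follow-up on either of two events, the first being "The subject undergoes a biopsy by 12 months, or". Section 8.4 summarises the ITD population by whether biopsy was immediate, delayed or never done. Section 8.1.1 treats an unbiopsied woman as disease-free on the strength of a negative 12-month clinical and imaging follow-up.

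**The concern.** These two sentences decide who is counted. Specificity is the primary endpoint and sensitivity the secondary one, and their denominators are the benign and cancer columns of the 8.5 table.

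The 8.5 exclusion says the opposite of rule 3 a few lines below it. The 8.3 definition, on its face, has no place for a cancer biopsied in week 2: there was no biopsy at month 12, and follow-up ended at the biopsy, so no TN or FP status is declared at month 12. Section 9.12 says the analysis plan is to follow the protocol's statistical section, so a defect here can carry into the programmed analysis sets.

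**Working it through.** **Step 1. The 8.5 exclusion as logic.** Let F mean followed and E mean evaluated. The sentence excludes an unbiopsied woman when NOT (F and not E). Rule 3 and 8.1.1 imply exclusion when not E.

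| Unbiopsied woman | Literal 8.5 | Rule 3 / 8.1.1 | Gets a column under the column rules? |
|---|---|---|---|
| Followed and evaluated after 11 months | excluded | kept | yes, if not already excluded |
| Followed, not evaluated | not excluded | excluded | no, there is no 11-month evaluation |
| Not followed at all | excluded | excluded | no |

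Read literally, the sentence removes the first group, and the column rules remove the second. No unbiopsied mass is left in the table. Under rule 3 an unbiopsied mass can only be TN, FP or left out, so the effect falls on specificity and cannot change sensitivity.

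**Step 2. The 8.3 population against the other sections.**

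| Mass | Literal 8.3 | 3.4, 8.4, and 8.5 rules 1-2 |
|---|---|---|
| Immediate biopsy, cancer | out | in |
| Immediate or delayed biopsy before month 12, benign | out | in |
| Biopsy at month 12 | in | in |
| No biopsy, TN or FP at month 12 | in | in |

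Sections 3.1 and 3.4 end follow-up at a biopsy, and 8.1.1 plans no study follow-up after it, so an early-biopsied mass cannot qualify through the 12-month status. Section 6.2.2 defines the Biopsied Group as women with BI-RADS 4 or 5 masses recommended for biopsy at entry. Most biopsy-proven cancers and biopsied benign masses would therefore be expected to fall in the first two rows. This sentence is the only one of the two that touches sensitivity.

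Applied together, the two literal readings would leave only masses biopsied at month 12.

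**Step 3. The plan's own figure.** Table 6 gives 860 benign masses. Inputs: d = 0.06, discordance η = 0.20, power 90%, 0.5% one-sided (the two-sided 1% of 8.1.1).

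- McNemar without continuity correction: n = (z₀.₉₉₅√η + z₀.₉₀√(η − d²))² / d² = (2.576 × 0.4472 + 1.282 × 0.4432)² / 0.0036 ≈ 822. Power at 860 is 91.5%.
- With continuity correction: power = Φ{[(d − 1/n)√n − z₀.₉₉₅√η] / √(η − d²)}. This first reaches 90% at n = 855. At 860 it is Φ(1.294) = 90.2%.
- Exact conditional test at 860: 90.8%.

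The continuity-corrected version reproduces 860 closely enough. The figure is not in dispute, and correcting the two sentences does not change it.

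**Step 4. What the literal 8.5 sentence could cost.** The protocol requires at least 1,000 benign masses and does not say how many will be unbiopsied. The shares below are assumptions. Power uses the continuity-corrected formula and, like Table 6, one set of pairs with no reader variance.

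| Assumed unbiopsied share of 1,000 | Benign masses left | Power for the 6% difference |
|---|---|---|
| 0% | 1,000 | 94.6% |
| 10% | 900 | 91.7% |
| 20% | 800 | 87.5% |
| 40% | 600 | 73.4% |
| 50% | 500 | 62.8% |

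No comparable figure can be given for 8.3, because the protocol does not split cancers or benign masses by time to biopsy.

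**The case against.** The strongest reply is that nobody would build the literal sets. Rules 1 and 2 accept a biopsy at any time. Section 8.4 describes the ITD population by immediate, delayed and no biopsy, which would be nearly pointless if 8.3 had already removed the first two groups. The tables planned in 8.5 would be almost empty. An ordinary reader takes 8.3 to mean biopsy status as of 12 months, and can read the 8.5 sentence loosely as excluding women who were not followed and had no later evaluation. Much of this stands: the intended set is largely recoverable, and that limits the size of the point.

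It does not make the sentences right. The loose reading of 8.5 needs a comma that is not there. On the unbiopsied, the surrounding text is also not of one mind. Rule 3 and one paragraph of 8.1.1 require the 12-month evaluation. A later paragraph of 8.1.1 treats the decision not to recommend biopsy as evidence enough, 3.3 adds only that there be no new findings, and the synopsis mentions conventional ultrasound only if it was performed. The 8.5 exclusion is the sentence that should settle this.

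A reader might go further and infer that specificity would rest on women who were never evaluated, or that the exclusion is completely reversed. The documents do not support that. Women followed without an evaluation escape the exclusion but get no column, and women not followed at all are out on either reading. A reader might also infer that nearly all of the 420 cancers in Table 7, or the 360 in Table 9, would be lost. Those are planning sizes. The 30- or 45-business-day window in the protocol runs from scan to biopsy, and 3.4 and 6.2.4 provide a further scan before a later biopsy, so the window does not date biopsies from enrollment.

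**Conclusion.** The point holds as an internal contradiction in text that defines who is analysed. The 8.5 exclusion, taken at its word, removes the evaluated unbiopsied women whom rule 3 counts, and with the column rules it leaves no unbiopsied mass in the specificity table. The 8.3 definition, taken at its word, removes masses biopsied before month 12, against 3.4, 8.4 and 8.5 itself, and so affects both sensitivity and specificity.

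It is not established that the denominators will come out wrong, because the neighbouring rules largely show what was meant. The power range of 91.7% to 62.8%, against 94.6%, is conditional on the literal 8.5 reading, exactly 1,000 benign masses, and an assumed unbiopsied share of 10% to 50%. The text should be corrected; the design and the planned sample size are not affected.

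**What to change.** In 8.5, replace the exclusion sentence with: *Subjects without a biopsy will be excluded unless they had a subsequent clinical evaluation after 11 months post-baseline.* This agrees with rule 3.

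In 8.3, change the biopsy condition to: *a biopsy within 12 months of enrollment*. Leave the clause on subjects declared TN or FP at 12 months as it is. It should not be replaced by a requirement for a benign determination: rule 3 tabulates some unbiopsied masses with contrary findings as False-Positive, and such a requirement could drop them from the population.

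The cost is two wording changes, carried into the statistical analysis plan. No new data, no further reads and no change to sample size are needed.

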5.13. Blinding

Subjects will not be blinded to study procedures but will not have access to the Imagio evaluation result.

The investigator will have access to all conventional diagnostic ultrasound, mammography, and biopsy reports, but the interpretation of the Imagio evaluation will not be provided to the investigator. The investigator will also have the option to perform the color or power Doppler during the conventional ultrasound examination for research purposes. The Doppler information will not be used in the analysis of this study for determining the safety and effectiveness of the Imagio.

The 7 independent registration readers and the 3 other independent reimbursement readers per case will have separate access to the relevant images and videos used to make the decision to perform or defer a biopsy in addition to the Imagio diagnostic ultrasound image and opto-acoustic image. Imagio and IUS are regarded as the two most important image sets for comparisons; these will be the image sets to be reviewed by the registration readers. Mammography is regarded as the most likely referral methodology and will be read alone and in combination with CDU and Imagio by the reimbursement readers. Readers will not have access to the background clinical information or to the histopathology report. The Truth Panel will have access to all clinical data, QA evaluator, and independent reader results to be able to alert the study medical monitor regarding any high risk subjects; the Seno study coordinator will in turn alert the study investigator in the event that the subject was not biopsied or the biopsy report was missing.

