6.4. Effectiveness Assessments

Blinded Imagio results will be transferred to the independent ICC that will review all screening and diagnostic imaging conducted including all Imagio results at baseline, prior to any biopsy (i.e. Month 6), and at Month 12 if no biopsy is scheduled. Any imaging studies performed after the Enrollment Visit but before the biopsy will also be forwarded to the ICC for independent reader review.

The histopathology report will be used to establish the diagnosis; if no biopsy is recommended at the Month 12 evaluation, then the Truth Panel will consider all imaging and pathology findings to decide if a True Negative determination can be made. .

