- Diagnostic referral to assess focal physical symptoms and / or signs that were either a chief complaint of the subject or were elicited by the healthcare practitioner (excluding focal breast pain in the absence of other positive clinical findings).
- Interval Clinical Problems (symptoms or physical findings excluding isolated focal breast pain, that have developed between yearly mammograms).
- Other referrals to diagnostic conventional ultrasound including subjects younger than 30 years old for a clinically suspicious area, or subjects referred from a screening MRI because of an

abnormality.

These subpopulations will be analyzed in aggregate as well as individually.

The Imagio diagnostic ultrasound component will serve as the "internal control".

The specificity determined by a 2% POM is the primary effectiveness endpoint while the sensitivity is the secondary effectiveness endpoint.

Multiple effectiveness endpoints will be assessed (one primary and four secondary) so the overall 5% Type I error will be controlled by requiring two-sided p=0.01 to establish statistical significance. Specificity will be tested first according to a superiority test while sensitivity will then be tested according to non-inferiority tests. Testing will be based on the specificity (primary endpoint) and sensitivity (secondary endpoint), both based on a 2% Probability of Malignancy (POM). The overall specificity exceeding 40% will also be tested. In addition, downgrading benign masses and upgrading malignant masses using Imagio relative to the site and relative to IUS will be evaluated.

The superiority test and the non-inferiority tests will each have at least 80% power to test their respective hypotheses according to a two-sided test with overall 1% Type I error. The histopathology findings of the biopsy procedure will serve as a gold standard for Imagio. The decision to not recommend a biopsy during the first 12 months together with a negative 12 month clinical and imaging follow-up and no evidence of a >20% increase in the mass will be regarded as evidence of no disease (True-Negative for a negative OA/FN for a positive screening OA) for those initially not recommended for biopsy.

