A total of 7 independent radiologists will be assigned per each case to independently evaluate both image sets (IUS and Imagio) per subject. In addition, 3 other independent readers will perform the reimbursement reads. All independent readers will evaluate all Pivotal Study cases; the readers will also review 5% of all cases to assess temporal trends and consistency; the initial evaluation will be used in all analyses.

Each registration reader will review the data from the two image sets (IUS, Imagio) for each case; each reader will evaluate Imagio according to a pre-determined diagnostic rule set based on OA image characteristics and will similarly evaluate IUS according to another pre-determined diagnostic rule set and each reader will estimate the probability that the mass is cancer on a scale from 0% to 100% in 5% increments (1% if \leq 10% or \geq 90%). Readers will assess IUS and Imagio in this pre-defined order during independent review sessions; this pre-defined order is consistent with medical practice.

Registration readers will also have access to the results of two locked nomograms to separately predict the POM and the probability of cancer. These nomograms were constructed from the Pilot Study cases using a linear model for the POM and a logistic regression model for the probability of cancer. The nomograms are constructed from the five feature scores for Imagio from a blinded review performed by [name]. The registration readers do not need to use the results of the nomograms in making their POM judgments, but they will immediately see the two predictions as soon as they score the five

features. The sensitivity and specificity of the nomograms will also be evaluated using the average predicted score; if the average is ≤ 0.1 , then the case is predicted to be benign.

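### Section 8.5 rule 3 contradicts Table 5 for unbiopsied masses: it fixes True-Negative and False-Positive labels against the test result, and lets the Imagio result decide whether a mass with contrary findings is analysed

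*Protocol*

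**What the plan says.** Section 8.5 fixes the cut-off: "the threshold for defining a positive POM will be 2% corresponding to clinical practice standards". Table 5 puts TP and FP in the test-positive row, and FN and TN in the test-negative row. On rows the section says "A subject will be assigned to a row in the table depending on the respective diagnostic test result". It introduces its numbered rules as the way a subject with a diagnosis receives a column. Separate tables are built for Imagio and for IUS.

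Rules 1 and 2 place biopsied masses by histology. Rule 3 covers masses not biopsied but evaluated after 11 months, and it has two halves:

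- (a) With no contrary findings the mass counts as TN. No POM condition is attached.
- (b) With contrary findings, which rule 3 says must not rest on Imagio, the mass "will be declared to be a False-Positive if the Imagio POM was ≤2%; otherwise the subject will not be included in the table".

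POM is a reader's score. In section 8.1.1 "each reader will estimate the probability that the mass is cancer on a scale from 0% to 100% in 5% increments", with finer steps at both ends of the scale, and seven registration readers each score both image sets.

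Three other places concern the same masses. Section 8.1.1 treats a negative 12-month follow-up as "evidence of no disease (True-Negative for a negative OA/FN for a positive screening OA". Section 8.3 admits unbiopsied masses that are "declared to be TN (or FP) at 12months". Section 6.4 says that if no biopsy is recommended at Month 12, "then the Truth Panel will consider all imaging and pathology findings to decide if a True Negative determination can be made".

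**The concern.** A 2x2 accuracy table works only if the reference standard sets the column and the test under study sets the row, independently of each other. Rule 3 breaks this in both halves.

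Half (a) assigns a cell, TN, where only a column (Benign) can be known. If that image set's POM is above 2%, Table 5 makes the mass FP.

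Half (b) calls a test-negative mass False-Positive, although a test-negative mass can only be TN or FN. It then drops the mass when Imagio is positive. Entry to the table therefore depends on the index test. Because POM is scored by reader, one mass can be in one reader's table and out of another's. The paired IUS table is also filtered by the Imagio result.

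The tables feed the specificity comparison (H1, primary) and stand-alone specificity (H3). If masses with contrary findings are cancers, they bear on sensitivity instead (H2, H4). As worded, the rule cannot be programmed consistently with Table 5.

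**Working it through.** The point disputes a classification rule, so there is no plan figure to reproduce first. The check sets rule 3 against Table 5 and then illustrates size on assumed counts.

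**1. Half (b), every combination.** Cut-off, cells and rule are from section 8.5.

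| Imagio POM | Row | Reference | Table 5 | Rule 3 |
|---|---|---|---|---|
| 1% or 2% | Test − | Benign | TN | FP |
| 1% or 2% | Test − | Cancer | FN | FP |
| 3% | Test + | Benign | FP | left out |
| 3% | Test + | Cancer | TP | left out |

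Rule 3 disagrees with Table 5 in every line. How a POM of exactly 2% is read does not matter, because 0% and 1% are negative either way.

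**2. The possible slips.**

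- Reading the condition as FP if POM is above 2% puts the masses in the Benign column (H1, H3).
- Reading the label as False-Negative if POM is at most 2% puts them in the Cancer column (H2, H4).
- Under either reading the remaining masses are still left out because of their Imagio POM.

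**3. Half (a).** Let *u* be the share of benign masses that are unbiopsied with no contrary findings, and *S* the specificity by Table 5, assumed equal in all groups. Read literally, rule 3 gives *S*(1 − *u*) + *u*. At *S* = 40%, the H3 null value, assumed *u* of 5%, 10% or 20% gives 43.0%, 46.0% or 52.0%. The protocol does not give *u*.

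**4. Half (b), stand-alone specificity.** Inputs from Table 8: 1,160 benign masses at 45%, so 0.45 × 1,160 = 522 TN. Assume *k* further masses, all benign and Imagio-negative.

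- *k* = 10: recorded as FP, 522/1,170 = 44.6%. Recorded as TN, 532/1,170 = 45.5%. Gap 10/1,170 = 0.9 points.
- *k* = 20: recorded as FP, 522/1,180 = 44.2%. Recorded as TN, 542/1,180 = 45.9%. Gap 20/1,180 = 1.7 points.

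**5. Half (b), paired difference.** Input from Table 6: 860 benign pairs, planned difference 6 points. Let *m* of the *k* masses be IUS-positive. Under Table 5 the *k* masses add *m* to the count of Imagio TN minus IUS TN.

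- FP label in the Imagio table only: they add −(*k* − *m*). The shift is *k*/(860 + *k*): 10/870 = 1.1 points, or 20/880 = 2.3 points.
- FP label in both tables: they add 0. The shift is *m*/(860 + *k*), anywhere from 0 up to those same values.

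The wording does not say which applies, so the range is 0 to 1.1 or 0 to 2.3 points.

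**6. If the masses are cancers.** Input from Table 7: 420 cancers. Assume 95% sensitivity in the rest, *k* cancers that are unbiopsied with contrary findings, and a share *q* of those Imagio-negative. Table 5 gives [0.95(420 − *k*) + (1 − *q*)*k*]/420.

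- *k* = 10, *q* = 20%: (389.5 + 8)/420 = 94.6%.
- *k* = 20, *q* = 50%: (380 + 10)/420 = 92.9%.

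Rule 3 gives 95.0% in both cases, because the false negatives move to FP and the true positives are left out.

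**7. Section 8.1.1.** A mass with no evidence of disease and a positive OA is test-positive and benign. Table 5 makes it FP, and section 8.3 allows TN or FP for such masses. Section 8.1.1 calls it FN.

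**The case against.** The strongest reply is that this is loose drafting with little reach. Masses biopsied within 12 months, including those biopsied for interval findings, fall under rules 1 and 2, so half (b) probably touches few masses. The protocol also often uses True-Negative to mean a benign reference status (synopsis under Control, sections 3.3 and 6.2.5). On that reading half (a) only assigns the Benign column. Section 8.3 already allows some reader-specific exclusions.

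Part of this stands. Half (b) is probably rare, and the charitable reading of half (a) is available. It does not rescue the rule. Section 8.1.1 ties True-Negative to a negative OA, so the term carries two meanings. False-Positive cannot be a reference status at all. The exclusions in section 8.3 concern case and image problems, not POM. Leaving the matter to the statistical analysis plan does not help either, since section 9.12 requires that plan to follow this statistical section.

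Four stronger readings are tempting, and the documents do not support them:

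- **No reference truth exists for these masses.** Section 5.5 has the Truth Panel record a benign or malignant classification and a True-Negative designation, and section 6.2.5 uses the Panel to establish mass change.
- **The Panel's access to reader results contaminates the column.** Section 5.13 does say "The Truth Panel will have access to all clinical data, QA evaluator, and independent reader results", but the purpose stated there is alerting on high-risk subjects, and rule 3 bars Imagio as the basis for contrary findings. Section 6.4 needs aligning with that bar; this is not evidence of a blinding failure.
- **The paired difference shifts by a fixed amount whatever IUS shows.** That holds only if the FP label applies in the Imagio table alone.
- **H3 passes by construction through half (a).** The row sentence in section 8.5 and the FP option in section 8.3 point the other way, and the unbiopsied share is not given.

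**Conclusion.** Rule 3 is wrong as written in both halves, and no other section overrides it. The conclusion rests on the protocol's own definitions, not on a demonstrated bias.

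The net size and direction of any bias are unknown, because the protocol gives no count of unbiopsied masses with or without contrary findings. Read literally, half (a) can only raise specificity. Half (b) mostly lowers Imagio specificity if the masses are benign, and hides false negatives from sensitivity if they are cancers. The point and percentage figures under the check depend on assumed counts and are illustrations only.

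Half (a) probably covers more masses than half (b). Correcting the inequality or the label in half (b) would not be enough, because exclusion would still depend on the index test. The FN label in section 8.1.1 is a related error. The rule should be rewritten before the tables are programmed.

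**What to change.** Rewrite rule 3 so that the column comes from the reference standard alone. Set the row separately for Imagio and IUS from each set's own POM, with 2% or less negative and above 2% positive:

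- **Not biopsied, no contrary findings at 11 months or later:** Benign column.
- **Not biopsied, contrary findings:** column by the Truth Panel's existing benign or malignant determination, not based on Imagio, as rule 3 already requires.
- **Indeterminate after Panel review:** excluded from both image sets and for all readers regardless of POM, with a sensitivity analysis that counts all such masses as benign and then all as cancer.

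In section 8.1.1, change the FN label for a positive OA with no evidence of disease to FP. Reconcile sections 5.5, 6.2.5, 6.4, 8.1.1, 8.3 and 8.5 so that True-Negative is either a table cell or a reference status, but not both.

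The cost is wording changes and one sensitivity analysis. No new data are needed.
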